The study is a parallel, single-blind, controlled, superiority trial in which participants will be randomized to a restrictive or a liberal transfusion group. This study will randomize 1520 Veterans at 15 VA Medical Centers. The total recruitment period will be approximately 4 years which will be followed by a 3 month active and 9 month passive follow-up period. The duration of the study will be approximately 5 years. Consent for the study will be obtained prior to the index surgical intervention at the clinic visit or, in case of inpatients, at the hospital ward pre- or postoperatively. Randomization will be performed via a central telephone randomization system once the participant has a confirmed Hb < 10gm/dl. Active follow up will be up to three months

after randomization. Passive follow up will be from 3 months to one year after randomization. The study flow is shown in FIGURE 3. There will be no blinding at the treating physician level; however the participants and the Endpoint Committee will be unaware of group allocation.

Follow up forms will be filled out during two postoperative clinic visits that will be after the 30th and 90th post-randomization days. Participants who cannot make the clinic visits will be assessed by phone call follow-up, during which they will be asked specific questions to ascertain whether signs or symptoms related to any of the endpoints have developed. In addition, the electronic medical record, will be assessed to collect relevant information. If a participant gets re-admitted at any time after discharge and within 90 days after randomization, the electronic medical record will be examined for the presence of any of the diagnoses that consist part of either the primary or any other endpoints. If the participant has been admitted to a non-VA facility, a full copy of hospital records from that admission will be obtained and assessed for the presence of any of the outcomes. History and physical, consultation notes and progress notes will all be reviewed. Furthermore, particular attention will be paid to laboratory reports for troponin, creatinine, CK-MB (if available), and WBC levels, reports of cardiac echograms, radiology reports, and results of cultures (blood, wound, sputum). Participant agreement for release of information to the study personnel for all postoperative hospital visits that occur within 90 days after randomization will be obtained as part of the original consent form.

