Participants will be given an appointment for a clinic visit within one week after the 30 post-randomization day. Questions regarding symptoms related to MI, other cardiac events, stroke, pneumonia, and wound infection will be asked. If a participant has a readmission prior to the 30 day post-randomization time point, then the electronic medical record, will be reviewed to determine whether the reason for admission includes any of the complications that consist of the primary or other study endpoints, such as coronary revascularization or acute renal failure. If the participant has been admitted to a non-VA hospital, then complete records from this admission will be obtained from that hospital to document the reason for admission and whether any of the study endpoints have been developed which led to the readmission. The hospital records obtained will include History and Physical, all consultations, procedures, laboratory values, fluid cultures, copies of EKG and Echocardiography reports, as well as reports from all imaging studies performed, catheterization laboratory reports and operating room reports. To assure access to these records, release of information forms will have to be signed by the participant as part of the initial informed consent process. If the participant does not present for the follow up within two weeks from the anticipated appointment time, an electronic medical record review and phone call follow-up will be performed and focused questions will be asked, to identify the occurrence of any of the endpoints. Questions about interval readmission will also be asked at the follow up visit/call.

b) Ninety Day Follow-up

Participants will be given a clinic appointment within two weeks after the 90th post-randomization day. Questions regarding symptoms related to cardiac events, stroke, infectious complications will be asked as described above for the 30-day post-randomization follow up. If participants are unable to make the clinic visit within two weeks of the assigned appointment then an electronic medical record review and phone call follow-up will be performed as described above. Readmissions since previous follow-up will also be investigated with similar series of actions as with the 30 day post-randomization follow-up. Pertinent laboratory values (creatinine, troponin), EKG results, cardiac catheterization reports and operating room reports since the previous visit will be

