The active follow up period for study purposes will be up to 90 days after randomization. If the participant refuses to continue participation during active follow up, his or her participation in the study will be terminated. All participants who complete the active follow-up phase of the study will be followed up to one year by the Chair's Office to assess mortality using a combination of phone call follow-up, search of the DAF, or electronic medical record

assessment. If a participant declines to participate in long term follow up then one year mortality data for this participant will not be collected. Given that the one year follow up is passive and does not involve any participant action we do not anticipate this to become a major issue.

X. TRANSFUSION STRATEGIES

Participants will be randomized to a liberal (transfuse if Hb <10 gm/dl) or restrictive (transfuse if Hb <7gm/dl) transfusion groups. Transfusion will be administered in order to maintain Hb just above the aforementioned thresholds for the index hospital stay or up to 30 days after randomization, whatever comes first. A participant must be randomized within 24-hrs of the first postoperative Hb falling below 10 gm/dl. It is strongly recommended that the transfusion treatment is initiated as soon as possible after and no longer than 24 hours from identifying a protocol-required transfusion Hb threshold. Transfusions will be administered according to the following scheme.

- A. Liberal group (transfusion trigger: Hb < 10 gm/dl)
 - i. If Hb < 7.5 gm/dl transfuse three units PRBCs, then check Hb. Based on the return Hb value, follow the transfusion protocol (steps i, ii, or iii) until Hb \geq 10.
 - ii. If $7.5 \leq$ Hb < 8.5 gm/dl transfuse two units PRBCs, then check Hb. Based on the return Hb value, follow the transfusion protocol (steps i, ii, or iii) until Hb \geq 10.
 - iii. If Hb \geq 8.5 gm/dl transfuse one unit PRBCs, then check Hb. Based on the return Hb value, follow the transfusion protocol (steps i, ii, or iii) until Hb \geq 10.
- B. Restrictive group (transfusion trigger: Hb < 7 gm/dl)
 - i. If Hb < 5.5 gm/dl transfuse of two units PRBCs, then check Hb. Based on the return Hb value, follow the transfusion protocol (steps i, or ii) until Hb \geq 7.
 - ii. If $5.5 \leq$ Hb < 7 gm/dl transfuse one unit PRBCs, then check Hb. Based on the return Hb value, follow the transfusion protocol (steps i, or ii) until Hb \geq 7.

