4.3. Randomization and Blinding

The clinical site coordinator will track the participants' postoperative Hb levels and identify participants whose Hb level is below 10 gm/dl and therefore eligible for randomization. iStat hemoglobin values may not be used as the basis for randomization/transfusion decisions. The CSPCC staff will prepare randomization schedules for each clinical site participating in the study. The study randomization to either liberal or restrictive transfusion policy will be done by an Interactive Touchtone Telephone Randomization System (ITTRS). A stratified block randomization scheme with block sizes of 2 and 4 will be used to randomize participants in the two transfusion groups. The stratifying factors are clinical site and revised cardiac risk index

(RCRI) class. The participants and the Endpoint Committee will be unaware of treatment group allocation.

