7.1. Primary Endpoint Analysis

The primary study endpoint will be a composite outcome of all-cause mortality, MI, coronary revascularization, acute renal failure, or post-randomization stroke within 90 days from randomization. A clinical events committee will adjudicate all component events for the primary endpoint. The number and percentage of participants with the composite endpoint at the 90-day visit after the randomization will be summarized and compared according to assigned transfusion strategy (analysis by intent to treat) using Pearson χ^2 test. Another analysis will compare primary endpoint between the two transfusion strategies stratified by clinical sites using the Cochran-Mantel-Haenszel test (Table 16a-e). The test for differences between transfusion strategies in the primary outcome will be conducted at an overall α -level of 0.05. Additional analysis will be conducted using logistic models to adjust for other clinical factors, such as age, RCRI, and nadir Hb. The interactions of the intervention with age, RCRI and nadir Hb will also be considered.

Odds ratio and 95% confidence interval (CI) will be presented using SAS PROC GENMOD or PROC LOGISTIC. Assumptions of the model including linearity in the logit of the composite event risk for continuous variables will be checked. We will assess goodness-of-fit using the statistic -2 log likelihood, which has a chi-square distribution under the null hypothesis that all the explanatory variables in the model are not associated with the outcome

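### Participant blinding is claimed but unsupported: entry at Hb below 10 plus the arm triggers make allocation largely inferable, and no concealment is described

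*Protocol*

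**What the plan says.** Protocol VI gives the design: "The study is a parallel, single-blind, controlled, superiority trial". It then separates the roles. For clinicians, "There will be no blinding at the treating physician level"; "however the participants and the Endpoint Committee will be unaware of group allocation". SAP 4.1 repeats the label and the statement, and SAP 4.3 says: "The participants and the Endpoint Committee will be unaware of treatment group allocation".

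On entry, Protocol VI says: "Randomization will be performed via a central telephone randomization system once the participant has a confirmed Hb < 10gm/dl". Protocol X defines the arms: "liberal (transfuse if Hb <10 gm/dl) or restrictive (transfuse if Hb <7gm/dl) transfusion groups". Under the liberal scheme any Hb below 10 leads to at least one unit, and starting within 24 hours of identifying the threshold is strongly recommended. Under the restrictive scheme no unit is due until Hb is below 7. Rapid bleeding is an exception in either arm, and after an MI the site may depart from the assigned scheme.

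On masking, Protocol X has a label placed at the room that identifies a transfusion study but not the arm. Protocol IX.C.1 has the arm written in a chart note. Neither document describes a screen, a sham or any check of blinding.

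On outcome assessment, Protocol IX.C.2 says of the 30-day visit: "Questions regarding symptoms related to MI, other cardiac events, stroke, pneumonia, and wound infection will be asked". The 90-day visit is similar. SAP 7.1 says: "A clinical events committee will adjudicate all component events for the primary endpoint". SAP 7.2, on secondary endpoints, does not mention adjudication. Protocol XVII.B makes the Endpoint Committee responsible for adjudicating outcomes in general terms, without listing which.

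**The concern.** Whether blood is given in the day or so after randomization depends directly on the arm, and a participant who is awake can see it. The documents therefore state a property that their own treatment scheme works against, and they give no procedure to preserve it.

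Two things are at stake. First, a report that calls the trial single-blind would claim protection from participant-side reporting bias that the plan does not provide. Second, the infectious and cardiac composites carry hypotheses in favour of the liberal arm, and each is tested at 0.01. Protocol X gives the Study Coordinator a part in running the transfusion scheme, and Protocol IX.D.1 has the site coordinator complete missed-visit assessments. The person recording these events may therefore know the arm. Two components have a softer criterion: wound infection can be met by pus drainage alone, and sepsis by two SIRS criteria with a source that is only suspected (Protocol V.B, SAP 3.2.2).

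**Working it through.** The plan gives no figure for masking, so there is none to reproduce on this point. The only plan figure used below is the arm size: 1444 / 0.95 = 1520, or 760 per arm (Protocol XVI.B), which is consistent.

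**Step 1. What each arm is due at entry.**

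| | Liberal | Restrictive |
|---|---|---|
| Hb at randomization | below 10 | below 10 |
| Trigger | below 10 | below 7 |
| Due at entry | at least one unit | none, unless already below 7 |

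Essentially every liberal participant treated to protocol is due a transfusion soon after randomization.

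**Step 2. How well transfusion status predicts the arm.** Let L be the share of liberal participants transfused after randomization and q the share of restrictive participants. With 1:1 allocation and the guess liberal if transfused, otherwise restrictive:

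correct guesses = (L + 1 − q) / 2

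This equals 50% only if L = q. The documents give neither L nor q. Protocol XVI.A expects restrictive nadirs of 6 to 9 gm/dl, a range that straddles the trigger of 7, so q must be varied widely. All inputs in this table are assumed:

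| | q = 5% | q = 20% | q = 50% |
|---|---|---|---|
| L = 100% | 97.5% | 90% | 75% |
| L = 95% | 95% | 87.5% | 72.5% |
| L = 90% | 92.5% | 85% | 70% |

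For example, (0.90 + 1 − 0.50) / 2 = 0.70 and (1.00 + 1 − 0.05) / 2 = 0.975.

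**Step 3. Sensitivity of a secondary test to uneven recording.** Take a pooled two-sided z-test at 0.01 with 760 per arm and no true effect, where one arm over-records events by 20% in relative terms. The true rates are assumed, because the documents give none for these composites.

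- True rate 10%, recorded 12% against 10%. Null SE = √(2 × 0.11 × 0.89 / 760) = 0.01605. Critical difference = 2.576 × 0.01605 = 0.0413. SE under the recorded rates = 0.01604. Then (0.0413 − 0.02) / 0.01604 = 1.33, and the rejection probability is 9.2%.
- True rate 25%, recorded 30% against 25%. The same steps give (0.0590 − 0.05) / 0.02287 = 0.39, and the rejection probability is 34.7%.

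Both compare with a nominal 1%. This shows what a given imbalance would do. It does not estimate the imbalance in this trial.

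**Step 4. Which secondary definitions leave room.** Pneumonia already requires imaging, arrhythmia requires EKG findings and new treatment, and CHF requires radiological evidence and a treatment change. Pus-only wound infection and suspected-source sepsis are the components that a stricter version would change.

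**Step 5. Whether the committee's own masking is supported.** Protocol X lists Hb results among the material that supports adjudication, and Protocol IX.C.1 puts the arm in the chart. No redaction is described.

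**The case against.** The best defence is that masking is weakened, not shown to be absent. Participants are not stated to be told their arm. Transfusion before or during the operation is allowed in both arms (Protocol VII.A), and one transfusion does not prove allocation. Consent may precede surgery and some participants are in intensive care, so being able to consent does not show that someone was alert when blood was given. Consent pages and the Operations Manual are not among the documents reviewed, so what participants are told cannot be seen. All of this stands. It pulls the figures in Step 2 towards 50%, but it does not supply a concealment procedure.

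A reader might infer more than the documents support:

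- *Few restrictive participants will be transfused, so the blind does not exist.* No restrictive share is given, and the expected nadir range straddles the trigger.
- *The SAP confines adjudication to the primary endpoint.* SAP 7.1 commits to the primary components but does not exclude others, and Protocol XVII.B is unrestricted. Adjudication of the secondary composites is unstated.
- *The secondary composites depend on participant blinding.* Most components rest on cultures, imaging, EKG or treatment changes, with record review behind the symptom questions. The larger exposure is to unblinded clinicians and site staff, and the protocol openly says that treating physicians are unblinded.
- *The primary result is compromised.* The primary endpoint is adjudicated and includes all-cause death. Nothing here shows bias in it.

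**Conclusion.** The concern holds as a fault in what the documents claim. The statement that participants will be unaware of allocation is unsupported by any described procedure and runs against the entry rule and triggers. Under the assumed ranges (liberal 90% to 100% transfused, restrictive 5% to 50%), transfusion status points to the right arm for about 70% to 97.5% of participants. This assumes that participants notice the transfusion and apply the simple rule.

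For the infectious and cardiac composites, masked adjudication is not stated either way. Their exposure comes mainly from site staff who know the arm, and it is sharpest for pus-only wound infection and suspected-source sepsis. The size of any resulting bias cannot be derived from the documents. The label should be corrected before results are reported; the primary analysis does not need to change.

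**What to change.** 1. In Protocol VI and SAP 4.1 and 4.3, replace the single-blind label and the statement about participants with: *open-label, with adjudication of primary-endpoint components masked to allocation*. If a concealment procedure does exist, describe it instead.
2. State whether the Endpoint Committee adjudicates the infectious and cardiac composites. Do not describe them as assessed unblinded unless the committee does not adjudicate them.
3. To support the masking that is claimed, withhold arm notes, transfusion records and Hb values from adjudication material, and reconcile this with Protocol X, which lists Hb as supporting material.
4. In SAP 7.2, add one sensitivity version of the infectious composite that drops wound infection based on pus drainage alone and sepsis with only a suspected source.
5. Report the share of participants transfused after randomization, by arm. The transfusion record is already collected, but none of the table shells in SAP Appendix 5 shows this.

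The cost is wording in two documents, redaction work and two tables from existing data. The downsides are a less favourable stated property, less clinical context for adjudicators and fewer events in the sensitivity version. That version also does not remove bias from unblinded decisions about when to culture or image.

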- c. Veterans with past medical history of ischemic stroke/TIA of likely carotid origin, or history of IHD, or history of PAD (defined as prior intervention for PAD or ABIs < 0.9) who undergo the following Vascular Surgery operations: Open aneurysm repair (including but not limited to carotid, subclavian, abdominal aortic, iliac, femoral, or popliteal aneurysms); and complex endovascular aneurysm repair (defined as fenestrated endograft, or endograft with need for iliac conduit, or endovascular aneurysm repair with simultaneous femoral artery reconstruction or bypass). Subclavian/vertebral bypasses and transpositions are eligible with a history of PAD/IHD/ischemic stroke.

Patients undergoing the above procedures will be included in the study regardless of their preoperative Hb level, and regardless of preoperative or intraoperative transfusion they might have received. For non-compressible arteries and patients with diabetes, toe pressures (<60 mm Hg) may be used to identify prevalence of PAD.

B. Exclusion Criteria

- 1) Veteran unable to consent
- 2) Veteran unwilling to follow protocol (such as Jehovah's witnesses)
- 3) Veteran with known history of hereditary anemias such as Thalassemia or Sickle cell disease
- 4) Veteran with known history of hereditary bleeding disorders, such as factor VIII or factor IX deficiency
- 5) Veteran with prior history of adverse reaction to blood administration, such as fever, rash, or hemolysis
- 6) Veteran does not speak or understand English
- 7) Veteran hemodynamically unstable (systolic blood pressure <90 and heart rate >100 that persists for at least 30 minutes) or in cardiogenic shock for ≥ 48 hours after the index procedure

- 8) Veterans participating in another interventional trial
- 9) Pregnancy in female Veterans
- 10) Veteran is a prisoner or in custody of law enforcement
- 11) Prior randomization in the CSP#599
- 12) Patients who are known to have tested positive for COVID-19 and have not recovered prior to consent will not be consented. Any participant who is known to have a positive COVID-19 test during the screening process and has not recovered will be excluded prior to randomization.

Recovery from COVID-19 is defined as a patient who is asymptomatic (per local preoperative clearance policies) and at least 10 days post a positive test.

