Note: Patients may be screened, consented, and randomized once recovered, if not previously randomized. Veterans who test positive *after randomization but before discharge* must be terminated for study ineligibility. Veterans who test positive *after randomization and after discharge from the index admission*, may continue to participate in the study as long as follow up is completed remotely.

C. Recruitment

The site coordinator along with the local site investigator (LSI) will be primarily responsible for identifying each potential participant scheduled for an open surgical procedure. At the beginning of the study, vascular and general surgeons performing the operations of interest at a VAMC will be personally contacted by the Site coordinator to discuss logistical and procedural issues related to recruitment. Surgeons (both vascular and general surgeons) have been contacted in 15 primary and 8 back up VAMCs and have confirmed interest in participation in the study.

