reviewed in the electronic medical record to ascertain the presence of coronary revascularization, stroke, MI, or acute renal failure.

c) One Year Follow-up

This will be follow up performed by trained staff from the Chair's office who will call all study participants at twelve months after randomization to ascertain vital status. The CSPCC will generate listings of participants due for follow-up which will be sent to the Chairman's personnel responsible for conducting the telephone interviews. Follow-up data will be obtained by study staff. This removes the need for personal identifying information to be maintained at the individual sites or the CSPCC and helps to protect participant confidentiality. Furthermore, chart reviews using the CAPRI/VistaWeb/JLV system will be performed as a participant's death and the date of death are typically documented in the electronic medical record. Access to the national electronic health record will be requested. The VHA Death Ascertainment File (DAF) will be used to assess the one year vital status of those participants discharged alive from the hospital for whom vital status cannot be determined. Social Security number will be used to obtain the patient identifier PatientICN, which will be necessary for linkage to the DAF. We will request DAF data for all participants that have been randomized in the study. All additional deaths identified through the DAF will be reported by study staff to the CSPCC staff in an electronic file.

D. Missed Visits and Termination

1. Missed Visits

If the subject fails to present to the clinic for follow-up visit, the site coordinator at the site will call the participant within 10 days to inquire about the reason for the missed visit and to reschedule the participant's appointment as soon as possible. If the participant still refuses to come for a clinic visit, the site coordinator will complete as much of the assessment as possible on the phone and using information from the electronic medical records. We anticipate issues with no-show for clinic visits to be minimal, as standard of care entails that participants need to present for frequent clinic visits after the major operations included in this study. Missed visits will be documented. The Site Coordinator will maintain a phone log that will include date, time, phone number called, reason for the missed visit, rescheduled date of clinic appointment, and/or reason for visit refusal.

2. Termination

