Active monitoring of reportable SAEs will begin as soon as randomization is complete and will end at 90 days after randomization or termination. The treatment plan includes follow-up outpatient visits of all participants for 3 months after randomization.

1. Expedited Reporting of Serious Adverse Events

All SAEs require prompt reporting to the CSP Coordinating Center and CSP Clinical Research Pharmacy Coordinating Center (CSPCRPCC) within 3 calendar days of the site investigator becoming aware of the event. The Pharmacist at the CSPCRPCC is responsible for evaluating all SAEs for participant safety concerns and/or regulatory reporting. The Pharmacist will consult with the Chairman's office during the review process, as necessary. The CSPCRPCC maintains a database of serious events for evaluation, by using the Medical Dictionary for Regulatory Activities (MedDRA) for coding and trending. Periodic summaries will be provided to the Data Monitoring Committee, the Study Chairman's office and Executive Committee (as necessary). Events that are determined to be serious, unexpected, and related to the study treatments will be reported to the site investigators, CIRB, and to the VA Cooperative Studies Program Central Office.

SAE Forms will be sent to the Perry Point CSPCC as directed. The CSPCRPCC will also have access to the information on the SAE Forms.

2. SAE Follow-up Reporting

If additional information is required the CSPCC or CSPCRPCC will fax or email a request to the site personnel reporting the SAE. The site should handle requests for SAE follow-up information in the same prompt manner that original SAE reports are handled. Serious adverse events should be followed to resolution, stabilization, or the participant's last active study contact, whichever occurs first. If an SAE is still ongoing by the time the SAE Form is submitted to the Perry Point

Transfusion Trigger after Operations in High Cardiac Risk Patients (TOP)

27

Version Number: 11 Date: 12/18/2024

CSPCC, complete an SAE Follow-up Form every 30 days until the SAE is resolved or stabilized. SAE Follow-up Forms will be sent to the Perry Point CSPCC as directed. The CSPCRPCC will also have access to the information on the follow-up SAE Forms.

It is the responsibility of the site investigator / coordinator at each participating site to know and comply with the SAE reporting requirements of the VA CIRB.

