Other Analyses 1. Baseline characteristics 2. Disposition status 3. Adherence 4. Age of Blood in relation to 90 day composite endpoint, wound Infection, and pneumonia 5. Time-to-event analyses for primary and secondary endpoints	1. Student t or Wilcoxon test, Pearson chi-square or Fisher test, 2. Pearson chi-square test 3. Pearson chi-square test 4. Pearson chi-square tests and Logistic regression 5. Log-rank test and Cox regression	1. PROC TTEST, PROC FREQ, PROC NP1WAY 2. PROC FREQ 3. PROC FREQ 4. PROC FREQ, PROC GENMOD 5. PROC LIFETEST, PROC PHREG

F. Criteria for Study Termination

There will be three interim analysis of the primary outcome measure performed in the study when 25%, 50%, 75% of the planned participants completed their participation in the study. If analysis of the primary outcome rates at the time of interim analysis indicates that the null hypothesis can be rejected the study will be recommended for termination for safety reasons.

G. Handling of Missing Data

Every effort will be made to minimize the occurrence of missing data, particularly for the primary and main secondary outcome measures. For the primary outcome, every effort will be made to contact the participants over the phone until participant termination. In the event of a potential drop out, every effort will be made to capture the primary outcome data from the VA databases. For participants who drop out during the study, multiple imputation (MI) method may be used for certain endpoint analyses. Multiple imputations will be based on Rubin's procedure using SAS PROC MI and PROC MIANALYZE. Sensitivity analysis will be performed to compare the results from the imputed data and the complete data without imputation.

H. Reporting of Any Deviations from the Original Statistical Plan

A more detailed statistical analysis plan (SAP) will be generated which will include the details of each statistical analysis plan for each outcome measure along with the suggested table shells for any reports that will be produced during the study and at the end of the study. Any deviations in the statistical plan from the protocol will be specified in the SAP. Any deviations from the SAP will be specified in a revised main manuscript which will be prepared and published at the end of the study.

XVII. STUDY ORGANIZATION AND ADMINISTRATION

A. Requirements for Participating Medical Centers

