5.2. Missing Data and Imputations

Every effort will be made to minimize the occurrence of missing data, particularly for the primary and main secondary outcome measures. For the primary outcome, every effort will be made to contact participants until subject termination. In the event of a potential drop out, every effort will be made to capture the primary outcome data from the VA databases. For participants who drop out during the study multiple imputation (MI) method may be used for certain endpoint analyses. Multiple imputations will be based on Rubin's procedure using SAS PROC MI and PROC MIANALYZE when missing is at random. Sensitivity analysis will be performed to compare the results from the imputed data and the complete data without imputation.

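### Participants who test COVID-positive in hospital after randomization must be terminated, which stops outcome contact and SAE monitoring although the ITT and Safety analyses still count them

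*Protocol*

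**What the plan says.** **Eligibility.** Exclusion 12 (Protocol VII.B) keeps out patients known to be COVID-positive and not recovered at consent. A participant found positive during screening who "has not recovered will be excluded prior to randomization". The Note that follows deals with later positives. Those between randomization and discharge "must be terminated for study ineligibility"; those after discharge may stay in if follow-up is remote. SAP 4.2 repeats exclusion 12 without the Note.

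**What termination ends.** For the primary outcome, "every effort will be made to contact the participants over the phone until participant termination" (Protocol XVI.G; SAP 5.2 is to the same effect). Active SAE monitoring "will end at 90 days after randomization or termination" (Protocol XI.D), and the Form 11 row of SAP Appendix 2 agrees. The text of SAP 4.4.3 instead runs monitoring to day 90 and does not mention termination.

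**Who is analysed.** Protocol XVI.E.1 puts everyone randomized into ITT and Safety, and ITT explicitly keeps drop-outs. SAP 5.4 removes only non-Veterans and previous participants from both sets. mITT, in both documents, removes people found to be ineligible.

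**What remains after drop-out.** "In the event of a potential drop out, every effort will be made to capture the primary outcome data from the VA databases" (SAP 5.2, with the same provision in Protocol XVI.G), and multiple imputation may be used. On deaths, Protocol IX.C.2.c states: "We will request DAF data for all participants that have been randomized in the study".

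**The concern.** A positive test after randomization breaches no criterion that applied when the participant was randomized. The participant has consented and has not refused follow-up. Even so, the rule turns off the two active collection streams, outcome contact and SAE monitoring, for someone whom the primary and safety analyses go on counting.

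At stake are the non-fatal components of the composite (MI, acute renal failure, coronary revascularization and stroke) and SAEs occurring between termination and day 90. The trial treats events at outside hospitals as worth pursuing: Protocol VI and IX.C.2 call for non-VA admission records. A fallback confined to VA databases may not see those events, and neither document gives a route for SAEs once a participant is terminated.

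**Working it through.** **1. Reproduce the plan's sample size.** Inputs from Protocol XVI.B and SAP 4.5: event rates 0.30 (restrictive) and 0.225 (liberal), two-sided alpha 0.05, power 90%, 1:1 allocation, 5% dropout.

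n per arm = [z(0.975)·√(2·p̄(1−p̄)) + z(0.90)·√(p1(1−p1) + p2(1−p2))]² / (p1−p2)²

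Here p̄ = 0.2625, the first root is 0.6222 and the second is 0.6200.

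n = [1.960 × 0.6222 + 1.2816 × 0.6200]² / 0.075² = 721.2, rounded up to 722 per arm, or 1444 in total. Then 1444 / 0.95 = 1520. Both figures match the plan.

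**2. Number affected (assumption).** The documents give no rate of in-hospital positives after randomization. I take 0.5% to 3% of 1520, which is 7.6 to 45.6 people (about 8 to 46). The dropout allowance is 1520 − 1444 = 76, so this group would use 7.6/76 = 10% to 45.6/76 = 60% of it.

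**3. Power if their outcomes are lost and treated as missing, equally by arm.**

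Power = Φ{[0.075·√n − 1.960 × 0.6222] / 0.6200}

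| Case | Evaluable per arm | Power |
|---|---|---|
| Within the 5% allowance | 722 | 90.0% |
| 0.5% on top of it | 760 × 0.945 = 718.2 | 89.9% |
| 2% on top of it | 760 × 0.93 = 706.8 | 89.4% |
| 3% on top of it | 760 × 0.92 = 699.2 | 89.1% |

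**4. A harsher case, for scale only.** Suppose all their events were missed and they were counted as event-free, equally by arm, with 722 per arm. Both rates are then multiplied by (1 − share).

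- 0.5%: 0.2985 against 0.2239, a difference of 7.46 points, power 89.8%.
- 3%: 0.2910 against 0.2183, a difference of 7.28 points (7.5 × 0.97), power 88.8%.

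**5. What is covered after termination.**

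| Item | Route after termination | Gap |
|---|---|---|
| Death | DAF data for all randomized (Protocol IX.C.2.c) | Little |
| Non-fatal components, VA care | VA-database capture (Protocol XVI.G; SAP 5.2) | Not stated by name for this group |
| Non-fatal components, non-VA care | Release of records for visits within 90 days, obtained at consent (Protocol VI) | Use after termination not stated |
| SAEs | None in Protocol XI.D or SAP Appendix 2; SAP 4.4.3 runs to day 90 | Documents disagree |

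**The case against.** The best reply is that the plan already has a fallback. ITT recognises two kinds of status, completer and drop-out, and SAP Tables 5 and 6 list several reasons for termination besides withdrawal. A participant terminated by rule is therefore a drop-out in the plan's own terms, and database capture and imputation apply. That stands. It would be wrong to infer that these participants have no outcome cover. What remains is narrower: non-VA non-fatal events, SAEs, and the absence of an express statement.

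Five other stronger readings are tempting, and the documents do not support them.

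- **That termination is reserved for refusal.** Protocol IX.D.2 says: "If the participant refuses to continue participation during active follow up, his or her participation in the study will be terminated". This names one trigger and does not call it the only one.
- **That unknown outcomes will be scored as no event.** The 0/1 coding in Protocol XVI.E.2 is ordinary model notation. It does not appear in the model text of SAP 7.1, and the missing-data sections point the other way. Step 4 is a bound, not a forecast.
- **That one-year deaths are lost.** Protocol IX.D.2 says "All participants who complete the active follow-up phase of the study will be followed up to one year", but it does not exclude others from the death-file request, so the two sections can be read together.
- **That removing these people from mITT is an error.** The Note itself calls them ineligible, so removal is a possible reading. The wording is open, and mITT is a secondary population.
- **That the loss must favour one arm.** The plan hypothesises a shorter stay under the liberal strategy, so time at risk of an in-hospital positive could differ. Nothing in the documents gives positivity rates, event timing or database completeness by arm, so neither a difference nor its direction can be shown.

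The reply is also right that the effect on power is small and that the reason for the rule is not stated. The consent form was not available for this review, so how far consent allows follow-up after a mandated termination could not be checked.

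**Conclusion.** The point holds as one of completeness. A mandatory rule triggered after randomization stops active outcome contact and SAE monitoring in people who were eligible when randomized, have not refused, and remain in the ITT and Safety populations. Database capture, imputation and the death file soften this but do not close it.

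The numerical cost is small: none if these participants fall within the 5% dropout allowance, and otherwise about 1 power point at most (90.0% to 89.1% as missing, 88.8% in the harsher case). Those figures rest on an assumed 0.5% to 3% share, equal loss by arm and the planned event rates. No bias is demonstrated. The change is worth making because the loss is avoidable with mechanisms that the protocol already contains. Confidence is medium, mainly because the number affected is unknown.

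**What to change.** 1. **Protocol VII.B Note.** Separate ending participation from ending ascertainment. Unless the participant refuses, continue remote and record-based collection of the primary endpoint and SAEs to day 90, as the Note already permits for post-discharge positives. Include non-VA records to the extent the original consent permits (Protocol VI), and use DAF for one-year vital status (Protocol IX.C.2.c).
2. **SAP 5.2 and 5.4.** Confirm that these participants stay in ITT, that the drop-out provisions apply to them, and that unknown outcomes are treated as missing. State whether a positive test after randomization leads to exclusion from mITT. Settle this before unblinded analysis.
3. **Separately, for every terminated participant.** Reconcile the end of SAE monitoring: Protocol XI.D and SAP Appendix 2 stop at termination, while SAP 4.4.3 runs to day 90.

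**Cost.** A protocol amendment that the VA Central IRB must review and approve (Protocol XVII.C.1), a few sentences in the SAP, and a little extra record review. No change to transfusion management is proposed.
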